COMIRB Protocol

**COLORADO MULTIPLE INSTITUTIONAL REVIEW
BOARD
[name] [contact]
[contact]**

Protocol #: 18-1854

Project Title: Evaluation of pancreatic cystic lesions via EUS-guided fine needle aspiration with and without micro forceps biopsies: A randomized controlled study

Principal Investigator: [name]

Version Date: February 5, 2021

I. Hypothesis: Evaluation of pancreatic cystic lesions using endoscopic ultrasound with fine needle aspiration (EUS-FNA) of cyst fluid and microforceps biopsies (EUS-MFB) has greater diagnostic yield and equivalent safety profile compared to EUS with fine needle aspiration (EUS-FNA) alone.

Specific Aims: To prospectively compare the efficacy and safety of EUS evaluation of pancreatic cystic lesions with 1) EUS-FNA plus MFB versus 2) EUS-FNA alone, in a randomized controlled study.

II. Background and Significance:

Pancreatic cystic lesions (PCLs) are a common incidental finding in cross sectional imaging (up to 27% on CT scan and 41% on MRI¹) and pose a management challenge to physicians. According to society guidelines,²⁻⁴ PCLs with specific features should prompt additional workup with endoscopic ultrasound (EUS) for cyst characterization as well as cyst sampling. This can help determine if the cyst is mucinous or non-mucinous which has implications for its malignant potential. Cyst fluid has traditionally been sampled using EUS with fine needle aspiration (EUS-FNA) and sent for fluid analysis and cytology. However, despite use of a cyst fluid carcinoembryonic antigen (CEA) level cutoff⁵ of 192 ng/mL and cytology, accuracy of diagnosis for PCLs is poor. As the spectrum ranges from benign to high risk for neoplasm, precise diagnosis is critical.

More recently, the adjunctive use of the Moray® through the needle microforceps biopsy (EUS-MFB) has shown promise for diagnosis of PCLs.⁶ This technology utilizes a microforceps through a 19-gauge

needle to biopsy the cyst wall for histology, in addition to collecting cyst fluid for CEA level and cytology. Only a few small retrospective reports have been published regarding the use of MFB.

D. Innovation:

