Pancreatic cysts continue to pose a management dilemma for practicing clinicians, especially with the increased use of radiologic imaging modalities identifying incidental pancreatic cystic lesions with higher frequency. This leads to patient anxiety and increased costs due to radiologic surveillance and even surgery. The results of this study will hopefully help increase diagnostic yield by obtaining a histopathologic diagnosis of these PCLs, and potentially affect practice patterns of gastroenterologists and the endoscopic community, specifically those physicians who perform EUS in these patients. Furthermore, the results will help determine whether there is reason to continue this line of research to obtain a definite histologic tissue diagnosis of PCLs.

III. Preliminary Studies/Progress Report:

We recently published our retrospective series of 27 patients using EUS-MFB for evaluation of PCLs and reported technical success of 100% and obtained a pathological diagnosis in 24 of 27 cases (yield 88.9%) with MFB. In 7 patients (26%), microforceps biopsy results drastically changed the diagnosis, providing diagnoses otherwise not suggested by cytology or cyst fluid CEA levels. However, cytology provided a diagnosis of mucinous cyst in 4 cases (14.8%) not detected by microforceps biopsies. No adverse events were noted.

Other small retrospective studies have shown that cyst fluid analysis via FNA is comparable to MFB for distinguishing mucinous from non-mucinous cysts, but MFB is better at diagnosing the specific cyst subtype.^{8,9} However, prospective data on the use and safety of MFB for PCLs is lacking.

IV. Research Methods

The study will be performed at 3 participating sites:

- (1) University of Colorado Hospital-Anschutz Medical Campus (UCH-AMC), Aurora, CO (Primary site)
- (2) Mt. Sinai Medical Center, New York, NY
- (3) University of California, Irvine, CA.

The study will be conducted after obtaining approval from the Institutional Review Board at all sites.

A. Outcome Measure(s):

Primary Outcomes:

A. Compare the efficacy and safety of EUS-FNA plus MFB, with EUS-FNA alone for evaluation of PCLs

Definitions:

A. Efficacy will be defined as technical and clinical success in performing MFB during EUS evaluation of PCLs.

(1) Technical success will be defined as the ability to puncture the cyst with the FNA needle under EUS guidance, advance the micro forceps into the cyst to perform cyst biopsies and obtain a visible tissue fragment.

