(2) Clinical success will be defined as the ability to obtain a pathologic tissue diagnosis of the PCL with MFB. Based on prior experience, expected diagnoses include pseudocyst, serous cystadenoma, mucinous cyst (mucinous cystic neoplasm, intra-ductal papillary mucinous neoplasm), adenocarcinoma, and neuroendocrine tumor, to name a few.

B. Compare safety of EUS-FNA plus MFB with that of EUS-FNA by recording adverse events per published ASGE criteria (10).

Secondary Outcomes:

A. Technical ease in performing FNA and MFB:

(1) Ease of passage of FNA needle

(2) Ease of passage of Micro Forceps

(3) Ease of EUS visualization of Micro Forceps

Technical ease will be scored on a predetermined 5-point Likert scale (1 = best, 5 = worst)

B. Time taken for FNA and time for MFB

B. Description of Population to be Enrolled:

Inclusion criteria:

- Adult patients >18 years old
- Cysts > 20 mm in size deemed appropriate for FNA by the endoscopist, based on clinical presentation, radiologic imaging features, associated solid mass or nodules, and patient anxiety about the diagnosis

Exclusion criteria:

- Age <18 years
- Inability to provide informed consent
- Thrombocytopenia (Platelets < 50,000) or coagulopathy (INR > 1.8)

- Pregnancy
- Post-surgical anatomy where the cyst is not accessible for FNA
- EUS findings suggesting that cyst FNA would be unsafe (e.g. intervening blood vessels)
- EUS appearance suggesting FNA is not indicated (e.g. cyst smaller than prior radiologic imaging, cyst not seen, EUS suggestive of serous cystadenoma)

C. Study Design and Research Methods

Patients will be provided the necessary information regarding the study and consent will be obtained either in person and/or electronically through medical records depending on specific site IRB approval guidelines. Patients will be randomized to intervention 1) EUS-FNA plus MFB or 2) EUS-FNA alone

D. Description, Risks and Justification of Procedures and Data Collection Tools:

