Use of fine needle aspiration as well as micro forceps biopsy for pancreatic cysts is safe with low rates of adverse events. Therefore, the risk to the patient is minimal. Additionally, accurate diagnosis is critical, as pancreatic cysts range from benign to malignant. Thus, comparing two interventions to evaluate cystic lesions to determine the optimal modality for diagnosis is justified.

Data collection will be carried out by the study team under the direction of the principal investigator. A REDCap database will be used to store clinical data information for subjects who consent to participate. This will serve as a clinical data repository for subject data. Clinical data will be extracted by the investigators or PRA from medical chart review. Access to the REDCap database will be granted by the study team, sometimes in limited fashion (e.g. no access to identifiers), to research staff and to co-investigators when needed. The final responsibility for the completeness and accuracy of all study data will belong to the principal investigator.

The study team will reach out to the subject at two different points post procedure.
1) Up to 72 hours post-procedure to collect data on the first 24 hours and
2) At day 30 to collect data AE data from the previous 30 days. Adverse events will be recorded per published ASGE criteria (10). The PI will continuously review local AEs and a safety officer not directly participating in the endoscopic procedures will review adverse events every 6 months. The PI will review serious device related events within 48 hours of the lead site becoming aware of the event. No serious adverse events were seen in our initial study (7) and in the study by Basar et al (9). Potential adverse events after these procedures include bleeding, perforation, infection, pancreatitis, and sedation-related complications, to name a few. Based on prior experience (7, 9) we do not expect a high rate of adverse events. Hence, we do not anticipate the need for an interim analysis.

E. Potential Scientific Problems: N/A

F. Data Analysis Plan:

The primary outcome of the study is to compare the diagnostic yield of the efficacy and safety of EUS-FNA plus EUS-MFB, with EUS-FNA alone for evaluation of PCLs.

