Descriptive statistics will be used to summarize the data. Continuous variables will be expressed as mean \pm standard deviation and categorical variables will be mentioned in percentages. T-test for continuous variables and Fisher's exact test or chi-square test for categorical variables will be used as appropriate.

Sample size calculation was performed as follows: to power the study to detect a 20% difference in efficacy would require enrollment of 76 patients in each group. However, after accounting for screen failures, technical failures in performing FNA/MFB based on actual findings during EUS where FNA/MFB would not be possible, patient drop out and loss to follow-up, we estimate 25% more patients would need to be included i.e. 102 patients would be needed in each group to get 76 patients in each arm who would actually get FNA/MFB. Statistical

analysis will be independently performed by intention to treat analysis by the University of Colorado Center for Innovative Design and Analysis, not by the PI

G. Summarize Knowledge to be Gained:

Most of the current data on evaluation of PCLs emphasizes the limitations in cyst sampling techniques and technologies. We are still far from being able to accurately diagnose many of these lesions. We have recently published results showing the safety and efficacy of the microforceps biopsy in a retrospective cohort, and much of the other data on MFB comes from case reports and small retrospective case series. There has never been a head to head trial comparing these two interventions. Additionally, there is no “standard” intervention and approach to PCLs is largely influenced by practice patterns among physicians as well as equipment availability. This is a prospective randomized controlled study that will help answer the question on which approach lends itself to more technical success and higher diagnostic yield while monitoring safety profile.

H. References:

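### No deciding primary outcome or success rule is stated, so the primary claim's type I error cannot be determined; both efficacy definitions also exclude the FNA-alone arm

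*Combined protocol and SAP*

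**What the plan says.** The combined protocol and SAP describes the primary outcome in several places, and they do not agree.

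- **Section I, Hypothesis.** EUS-FNA plus MFB "has greater diagnostic yield and equivalent safety profile compared to EUS with fine needle aspiration (EUS-FNA) alone". Technical success is not mentioned.
- **Section IV.A, Primary Outcomes.** The aim is to "Compare the efficacy and safety of EUS-FNA plus MFB, with EUS-FNA alone for evaluation of PCLs". On efficacy: "Efficacy will be defined as technical and clinical success in performing MFB during EUS evaluation of PCLs". Two numbered definitions follow. Technical success requires the operator to "advance the micro forceps into the cyst to perform cyst biopsies and obtain a visible tissue fragment". Clinical success is "the ability to obtain a pathologic tissue diagnosis of the PCL with MFB". Safety is then a separate item: "Compare safety of EUS-FNA plus MFB with that of EUS-FNA by recording adverse events".
- **Section IV.F, Data Analysis Plan.** "The primary outcome of the study is to compare the diagnostic yield of the efficacy and safety" of the two approaches. This puts yield, efficacy and safety into one sentence without ranking them. The sample size is 76 per group for a 20% efficacy difference, raised to 102. The tests are Fisher's exact or chi-square, as appropriate, by intention to treat.
- **Section IV.G.** The study is to show "which approach lends itself to more technical success and higher diagnostic yield", so technical success appears as a comparative result in its own right.

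No section gives an alpha, a power, base rates, a safety margin, a rule for combining the primary outcomes or a multiplicity adjustment.

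**The concern.** Two readings of the efficacy definition are open. One is a single outcome in which both successes are needed. The other is two outcomes, each tested separately. The plan does not choose, and it does not say how safety combines with efficacy. The primary claim could therefore be settled after the results are seen, and the independent analysis group named in IV.F would have to guess the endpoint and the rule. The 76 per group cannot be checked against the outcome that will decide the trial, because that outcome is not named.

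A further difficulty lies in the definitions themselves. Both efficacy outcomes are worded in terms of MFB, which only one arm receives, so the comparison between arms on them is settled by wording and not by data.

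**Working it through.** **1. The plan's own sample size.** For 76 per group, the usual two-proportion formula is n = [1.96·√(2p̄(1−p̄)) + 0.84·√(p₁(1−p₁)+p₂(1−p₂))]² / (p₁−p₂)². It assumes two-sided 5%, 80% power and a 20-point absolute difference, none of which the plan states.

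- 63% vs 83%: n = 76.2 without continuity correction.
- 68% vs 88%: n = 75.8 with continuity correction.
- 68.9% vs 88.9% (the upper rate is the 24/27 yield in section III): n = 73.8 with correction.

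Different base rates therefore give about 76, and the figure cannot be assigned to one outcome. The inflation step does reproduce: 76/(1−0.25) = 101.3, rounded up to 102.

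**2. Can the arms be compared as defined?** Section III reports 100% technical success and 88.9% diagnosis with MFB. In the FNA-alone arm both are 0% by definition, because no forceps is passed. The difference in clinical success would be 88.9 − 0 = 88.9 points, against a planned 20. No chance-only null applies to these definitions. Steps 3 and 4 therefore assume that the outcomes have been reworded so that both arms can reach them.

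**3. If all components must be met.** P(all significant) cannot exceed the smallest single-test probability, so the risk is at most the nominal 5%. If both successes are required per patient, nesting reduces efficacy to clinical success, which is one test at about 5%.

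**4. If a win on either efficacy outcome may count.** P(either) = P(T) + P(C) − P(both), where T and C are significant results on technical and clinical success. For reference, two independent tests give 1 − 0.95² = 9.75%. For nested outcomes I simulated 400,000 trials per setting with no true difference and 76 or 102 per arm. Clinical success was drawn only among technical successes, and each test was two-sided at 5%. Assumed rates were technical 80-95% and clinical 70-90% given technical.

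| Setting (technical; clinical given technical; n per arm) | Test | P(T) | P(C) | P(both) | P(either) |
|---|---|---|---|---|---|
| 80%; 90%; 102 (lowest) | chi-square | 4.9% | 5.1% | 2.2% | 7.8% |
| 90%; 70%; 76 (highest) | chi-square | 5.2% | 5.3% | 0.8% | 9.6% |
| 95%; 90%; 76 (lowest) | Fisher | 1.5% | 3.0% | 0.3% | 4.2% |
| 80%; 70%; 102 (highest) | Fisher | 3.3% | 4.0% | 0.7% | 6.6% |
| 100%; 88.9%; 76 (section III rates) | chi-square | 0% | 5.0% | 0% | 5.0% |
| 100%; 88.9%; 76 (section III rates) | Fisher | 0% | 2.8% | 0% | 2.8% |

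Entries are rounded separately, so rows may differ by 0.1. Allowing for simulation error, the ranges are about 8% to 9.5% by chi-square and 4% to 7% by Fisher. With 100% technical success in both arms, that test cannot reject and the excess disappears.

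**5. Direction.** These figures count false results in either direction. A false win for the MFB arm is about half as likely: 3.9% to 4.8% by chi-square over the 80-95% settings, against a nominal 2.5% for one test.

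**The case against.** The strongest reply is that the plan never says that one win is enough. The hypothesis joins greater yield to equivalent safety, and the efficacy definition joins technical to clinical success. Read that way, nothing is inflated. The plan also allows Fisher's test, and its only documented technical success rate is 100%. Under either of those conditions the two-outcome risk is close to or below 5%. Section IV.G describes the knowledge to be gained and is not an analysis rule.

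All of this stands. A reader might infer that the false-positive risk is well above 5%. The documents do not support that as a flat statement, because it needs an any-one-wins rule that they do not contain, together with chi-square tests and technical success below 100%.

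A reader might also add adverse events as a third test and arrive at 12% to 14% (chi-square, with a 6% event rate assumed). That is not a false-success rate. Safety is an equivalence aim, so a chance significant difference in adverse events would not establish the hypothesis. The gap on safety is the missing margin. The 6% is also not taken from the plan, which reports no events in 27 patients and expects a low rate.

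The reply does not supply the rule. A joint reading is plausible, but the text neither states it nor excludes the alternative. Nor does the reply answer the MFB-only definitions.

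**Conclusion.** The concern holds in this form: the deciding outcome, alpha and success rule are unspecified, so the type I error of the primary claim is undetermined. It is at most about 5% under a joint rule. If either efficacy outcome may count, it is about 8% to 9.5% by chi-square, about 4% to 7% by Fisher, and about 5% by chi-square with 100% technical success in both arms. The two-sided 5% level, the 80-95% and 70-90% rates and the nesting are assumptions. The figures also presume outcomes that both arms can reach.

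The definitions do not meet that last condition, so the arms cannot be compared fairly on either efficacy outcome as written. This part needs no assumption about rates and is the more serious of the two.

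**What to change.** In IV.A and IV.F:

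- Name one primary efficacy outcome that follows the hypothesis: diagnostic yield per randomized patient, meaning a diagnosis from any sampling done in the assigned arm. State what counts as a diagnosis by criteria that apply to both arms. Test it once at two-sided 5%, with the test named.
- Restate the 76 per group for that outcome, with the assumed rates, alpha and power.
- Make technical success secondary: the MFB step described in Group 1 only, and puncture and aspiration success compared between arms.
- Keep safety as the second part of the hypothesis, which must also hold against a margin stated in advance. Because both parts are required, no alpha split is needed.

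The cost is wording, with no new procedures. Technical success alone could no longer support the primary claim. The safety margin brings its own power calculation, and restating the sample size may show that 76 does not match the chosen outcome.

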Patients will be enrolled in this study when evaluated in GI clinics, hospital wards, and endoscopy suites. Consent for the study will be obtained either in person, by the interventional endoscopist who will be performing the procedure or by the research assistant/ study coordinator or electronically through medical records depending on specific site IRB approval guidelines. All UCH interventional endoscopists who perform EUS will participate in the study. All participating investigators are experienced interventional endoscopists proficient in EUS. Initial evaluation of patients will include collection of data on demographics, history, physical examination and pertinent radiologic, laboratory, and endoscopic data, and prior management/therapies. Details of previous endoscopic and surgical evaluation along with histopathology data will be documented, as needed for clinical care.

After obtaining informed consent, subjects will undergo EUS per clinical protocol. All procedure-related clinical decisions and interventions will be dictated by the performing physician as he or she sees fit. Once the pancreatic cystic lesion is seen and assessed by EUS, randomization will be performed after determination by the endoscopist and research coordinator that the patient meets inclusion criteria and does not have exclusion criteria.

A pancreatic cyst with high risk stigmata (presence of dilated main pancreatic duct > 10 mm, mural nodule or associated solid mass) would be referred for surgical resection based on patient's clinical status, irrespective of cyst fluid analysis/cyto/pathology. Cysts without high risk stigmata are followed with radiologic surveillance imaging in 1-3 years

Procedure description:

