Prophylactic antibiotics (Ampicillin-Sulbactam 3 g or Ciprofloxacin 500 mg intravenous) will be administered to all patients prior to needle puncture of the cyst, and for 3-5 days post procedure (Amoxicillin-Clavulanate or Ciprofloxacin orally) as per routine standard of care. A detailed endosonographic examination of the cyst will be performed using a curvilinear array echoendoscope (Olympus America, Center Valley, PA) as per routine clinical care. Careful evaluation will be performed for cyst location, size, presence of mural nodule, associated solid mass, and communication with the main pancreatic duct. Patients will then be randomized by a computer-generated algorithm to EUS-FNA plus MFB (group 1) or EUS-FNA alone (group 2). Histological diagnosis is considered a gold standard and a positive MFB diagnosis is considered a true diagnosis. Please note that currently we have been performing EUS-FNA and MFB for pancreatic cysts as part of routine clinical care and this is NOT considered experimental. This procedure does not have negative implications for insurance coverage, patient charges, and hence will not affect our budget. We will perform the procedure for patient care irrespective of the study.

(1) EUS-MFB plus FNA group:

The cyst will be punctured using a 19-G EUS-FNA needle with a stylet. A transgastric approach will be used for PCLs located in body/tail region, and a transduodenal approach for PCLs in the head/neck region, or as determined by the endoscopist. The stylet will be removed and the wall of the cyst biopsied using the micro forceps passed through the 19 G needle under direct EUS visualization. A minimum of 4 cyst wall biopsies will be obtained to procure at least 4 visible tissue fragments. Cyst fluid will be aspirated and sent for CEA and cytology.

(2) EUS-FNA alone group:

The cyst will be punctured using an EUS-FNA needle with a stylet. A transgastric approach will be used for PCLs located in body/tail region, and a transduodenal approach for PCLs in the head/neck region, or as determined by the endoscopist. The stylet will be removed, and cyst fluid will be aspirated and sent for CEA, and cytology.

UCH cytopathologists and pathologists experienced in pancreatic cytology and pathology will evaluate all cytology and micro forceps biopsy specimens per standard clinical care. Clinical follow-up will be obtained as per routine clinical care.

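### Needle-ease scores and FNA times come from several endoscopists at three sites, but the plan names only pooled two-sample tests, which leave any between-operator variance in the error term

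*Combined protocol and SAP*

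**What the plan says.** All references are to the combined protocol and SAP.

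- **Outcomes (IV.A, Secondary Outcomes).** The first ease item is "1) Ease of passage of FNA needle". The scoring rule is "Technical ease will be scored on a predetermined 5-point Likert scale (1 = best, 5 = worst". The second secondary outcome is "B. Time taken for FNA and time for MFB". Needle ease and FNA time exist in both arms. The two forceps items and MFB time exist only in the arm that receives MFB.
- **Operators (IV and IV.D).** "The study will be performed at 3 participating sites", and at the primary site "All UCH interventional endoscopists who perform EUS will participate in the study". Technique is left to the operator: "All procedure-related clinical decisions and interventions will be dictated by the performing physician as he or she sees fit".
- **Allocation (IV.D).** "Patients will then be randomized by a computer-generated algorithm to EUS-FNA plus MFB (group 1) or EUS-FNA alone (group 2". No stratification by site or endoscopist is stated.
- **Analysis (IV.F).** The plan names "T-test for continuous variables" and Fisher's exact or chi-square test for categorical ones, to be used as appropriate. It has no site or endoscopist term and no mixed or stratified model.

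The documents do not say who gives the ease score, how many endoscopists take part, or how much of the spread in score or time is expected to lie between operators. Only the two ends of the scale are labelled.

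**The concern.** Needle ease is a subjective rating, presumably given by the operator, and procedure time depends on who does the procedure. If endoscopists use the scale differently or work at different speeds, part of the variation in both outcomes belongs to the operator and has nothing to do with the arm. A pooled two-sample test treats that part as noise.

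What is at stake is precision. A real difference in needle ease or FNA time could be missed, or estimated with a wider interval than the data allow. Adjustment chosen after the data are seen is open to challenge, so the choice belongs in the plan. Adjustment also needs a record of who performed each procedure, and the data-collection text in IV.D describes no such field.

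**Working it through.** **The plan's own figures.** IV.F gives 76 analysable patients per group for a 20% difference in efficacy and 102 enrolled per group. The second follows from the first: 76 / (1 − 0.25) = 101.3, rounded up to 102. The 76 cannot be uniquely checked, because alpha, power and base rates are not given. It is attainable: two-sided 5% and 80% power give 77 at 63% v 83%, and 75 at 64% v 84%. No figure is stated for needle ease or FNA time, so 76 is used below only as the number per arm.

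**Inputs**
- n = 76 per arm (IV.F).
- Two-sided 5% level (assumed).
- Operator share of total variance, ρ: 0 to 0.30 (assumed).
- Number of endoscopists, K: 6, 12 or 20, of unequal volume (assumed).
- Arm difference: about 0.45 of the total SD (assumed, because it gives the pooled t-test about 80% power).

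**Step 1. Difference the pooled test can detect.** With total SD = 1 and 80% power:

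d = (1.96 + 0.8416) × √(2/76) = 0.454.

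**Step 2. Upper limit of the gain.** If all operator variance were removed at no cost, the SD would fall to √(1 − ρ):

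power = Φ( d / [√(1 − ρ) × √(2/76)] − 1.96 ), where d / √(2/76) = 2.802.

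| ρ | 2.802 / √(1 − ρ) | Power | Gain over 80% |
|---|---|---|---|
| 0.05 | 2.874 | 82% | 2 points |
| 0.10 | 2.953 | 84% | 4 points |
| 0.20 | 3.132 | 88% | 8 points |
| 0.30 | 3.349 | 92% | 12 points |

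**Step 3. What a strictly within-operator analysis costs.** Without stratified allocation, the arms are not balanced within each operator. With N = 2 × 76 = 152, the expected information retained is about (N − K)/(N − 1):

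- K = 6: 146/151 = 0.967
- K = 12: 140/151 = 0.927
- K = 20: 132/151 = 0.874

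Fixed operator effects break even where 1 − ρ equals this ratio: ρ of about 0.03, 0.07 and 0.13 respectively. Below that share they lose power. Simulated 5-point scores agree. Pooled t-test v fixed endoscopist effects:

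| ρ | K = 12 | K = 20 |
|---|---|---|
| 0.05 | 74% v 73% | 74% v 70% |
| 0.10 | 74% v 74% | 74% v 72% |
| 0.20 | 75% v 79% | 73% v 75% |

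**Step 4. Random intercept.** This model uses between-operator information when ρ is small and approaches the within-operator analysis when ρ is large. Simulation with 12 endoscopists and a 0.45 SD shift, pooled t-test v random intercept:

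| ρ | FNA time | 5-point score |
|---|---|---|
| 0 | 79% v 79% | 74% v 74% |
| 0.10 | 79% v 81% | 75% v 76% |
| 0.20 | 79% v 84% | 76% v 81% |
| 0.30 | 81% v 89% | 77% v 85% |

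Across 6, 12 and 20 endoscopists the gain is about 0 to 1 point at ρ = 0.05, 1 to 3 at 0.10, 4 to 7 at 0.20 and 7 to 10 at 0.30. There is no measurable loss at ρ = 0. These gains lie below the limit in Step 2, as they should.

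**Step 5. Validity.** With no arm difference, both methods reject in about 5% of simulated trials under simple randomisation.

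**The case against.** The strongest case against is that nothing here is an error. The pooled test is valid, and a covariate that might improve precision could be suggested for nearly any multi-operator trial. IV.A states no between-arm contrast for ease or time, IV.F begins with descriptive summaries, and the only power target is for efficacy. The scorer, the number of endoscopists, ρ and the 0.45 SD shift are all assumed. IV.D describes the investigators as experienced and proficient, which could mean a small ρ, where the gain is 3 points or less. All of this stands, and it limits the point to a modest gain in efficiency.

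A second objection is that adjustment can cost power. That is true of fixed effects and stratified rank tests when operators differ little or are numerous (Step 3). It does not apply to the random intercept (Step 4).

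A third is that the arm difference may itself vary by operator: IV.D names a needle gauge for the combined arm but not for the FNA-alone arm, and leaves procedural decisions to the physician. A random intercept does not address this, so that limit also stands.

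Stronger readings that a reader might infer are not supported:

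- **Clustering by endoscopist biases the comparison or inflates type I error.** Patients are randomised individually, so it does neither. Had allocation been stratified by operator, which the documents do not state, the pooled t-test would be conservative: simulated type I error is about 4% at ρ = 0.1 and 2% at 0.3.
- **There are many endoscopists and they are known to differ.** The documents support only several, and differences in scale use or speed are a reasonable assumption.
- **Needle-ease scores in the combined arm are coloured by later use of the forceps.** The documents do not say when the score is given. This is a separate question of bias, and nothing in the calculation bears on it.

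**Conclusion.** The point holds as one of efficiency. Several endoscopists at three sites contribute to the comparable secondary outcomes, and the named tests leave any between-operator variance in the error term. With 76 per arm and a 0.45 SD shift, the power forgone by pooling is negligible if operators account for 5% of the variance and 7 to 10 points if they account for 30%. These figures rest on a constant arm effect, individual randomisation without stratification, and an operator share that the documents do not give.

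The point does not touch the primary outcome or the sample size, and it does not show that the planned tests are wrong. Its importance is low. It is worth making because the remedy is cheap and costs no measurable power if operators turn out not to differ.

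**What to change.** In IV.F, pre-specify that needle-ease score and FNA time are compared between arms with a model containing arm and a random intercept for endoscopist. Low-volume operators are then kept in the analysis. FNA time can be analysed on the log scale if it is skewed. The gains above are for a linear model. An ordinal model with the same random intercept is an option for the score. The random intercept is preferred to fixed endoscopist effects or a stratified rank test, which can lose several points of power.

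Add an operator code to the REDCap record for each procedure, and state in IV.A who gives the ease score. If the scorer is not the operator, record the scorer as well.

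The cost is a sentence in IV.F, a clause in IV.A and a database field. No change to sample size, allocation or procedures is needed.
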